Surgical outcome will also be assessed via: 1) patient-oriented outcome scores^{59,76}, 2) AP laxity (an indicator of graft integrity^{6,44} and knee kinematics²³), 3) isokinetic strength (an indicator of dynamic knee function¹⁶), and 4) clinical outcome scores^{48,78}. Analysis of primary and secondary outcomes will enable us to determine the long-term effects of initial graft tension on cartilage status and knee joint function, and to evaluate the relationships between longitudinal changes that occur in tibiofemoral (TF) joint space (x-ray), cartilage thickness (MRI), general MRI scores (WORM score), knee laxity (KT-1000), strength (Biodex strength test, 1 legged hop test) and patient-oriented outcome scores (SF-36, Knee Osteoarthritis Outcome Score). In the past funding cycle, data were obtained from ACL-reconstructed patients pre-operatively, immediately post-operatively, and after 6, 12, 36, and 84 months of healing. From the control group data were obtained at the time of recruitment and at 12, 36, and 84 months. In this update, additional evaluations will be performed 144 and 180 months in the ACLR and control subjects, a time frame in which cartilage damage should become prevalent in the ACLR patient population. We intend to follow these patients for a minimum of 15 years.

RESEARCH DESIGN AND METHODS

1. Overview of Research Design

This investigation is designed as a prospective, randomized, double-blinded clinical study evaluating the effects of two different initial tension conditions applied to an ACL graft at the time of fixation on healing using biomechanical, clinical, and patient-oriented outcome measures. The primary outcome is evaluating the progression of OA via objective radiographic measurements of joint space narrowing. We are also assessing temporal changes in cartilage thickness, and the integrity of various knee joint structures using MRI. We will test the hypothesis that tibiofemoral (TF) joint space width (via radiography) and cartilage thickness (via MRI) in the reconstructed knees of the “high-tension” treatment group will be equal to that of the control group, while the joint space width and cartilage thickness in the “low-tension” treatment group will be significantly less than that of the control group 15 years after surgical reconstruction of the ACL. We intend to follow these patients for a minimum of 15 years.

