60 “matched” control subjects, who had no known history of knee injury or symptoms of arthritis, were recruited from the hospital campus, local colleges, and Providence community. They were selected to match the frequency of individuals by age (± 5 years), gender, race, and activity level (Tegner score ± 1 point). The subjects’ knees were evaluated by clinical exam at a screening visit. Subjects were not included in the control group if they have a side-to-side difference in AP laxity greater than or equal to 2-mm (KT-1000), a Tegner activity score less than 5⁶⁹, or if they meet any of the other exclusion criteria (Table 1). It was our intent to establish a control group that matched the characteristics of the population at risk to ACL injury.

3. Research Design

This study is designed as a prospective, randomized, double-blinded controlled trial comparing the outcome of two different initial tension conditions applied to the ACL graft at the time of surgery, and to determine the relationship between factors that may predict who will be risk for OA. The project statistician and the operating surgeon initially knew a patient’s assignment at the time of surgery, however, the

surgeon was not allowed to review the assignment once the surgery was completed, and the statistician was not allowed to review the assignments until after all the subjects were enrolled. The patient, the therapist performing the follow-up assessments, the AP laxity and isokinetic strength testing, the engineer performing the radiographic joint space width and cartilage thickness measurements, and the radiologist performing the WORM scoring will continue to be blinded from the subject's group assignment throughout the study. An intent-to-treat protocol is being utilized. All subjects randomized to each group are being followed, and all available data will be analyzed even if the graft fails, if the subject is unwilling to perform a particular follow-up test (missing data), or if a subject completely drops out of the study.

Table 1. Inclusion/exclusion criteria for patient enrollment.

Treatment Groups (Hi- and Lo-tension)	
Inclusion Criteria	Male or female subjects between the ages of 15 and 50 years with unilateral ACL injury.
	Candidates for ACLR using bone-PT-bone or four-stranded hamstring tendon autograft.
	A Tegner activity score ⁶⁹ ≥ 2 .
	Minor tears of the menisci that require minimal treatment (<1/3).

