Treatment Comparisons - Primary Outcome Measure: Repeated measures analysis of variance will be used to evaluate differences among treatment groups with respect to temporal changes in joint space width (i.e. joint space narrowing). The statistical model will include fixed factors representing treatment group (“low-tension”, “high-tension” and “control”), limb (operative vs. contra-lateral or two controls), location (medial vs. lateral), time (baseline, 12-, 36-, 60-, and 84-month), and their interactions. If significant interactions are detected, simple effects will be compared using the Student-Newman-Keuls procedure based on the appropriate error terms⁸⁰. Because one of the repeated factors (i.e. time) is quantitative, orthogonal polynomial will be used to partition the time effect into its individual quantitative components (i.e. linear and quadratic). The significance of these orthogonal contrasts will be used to evaluate the linearity (or non-linearity) of the temporal trend associated with degeneration. Analyses will be performed using SAS, PROC MIXED⁵² that allows for covariance structures other than compound symmetry (e.g. unstructured, autoregressive, spatial power law). It is expected that the variability across subjects may increase across time due to only a subset of individuals exhibiting degeneration, which would violate the standard homogeneity of variance assumptions. The normality assumption will be examined based on residuals using normal probability plots and the Wilk-Shapiro test. If necessary, data will be transformed prior to analysis in order to satisfy the distributional assumptions.

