Justification of Sample Size based on Primary Outcome Measure: The estimated sample size of 35 assessable subjects per group through the 84-month study period will result in having sufficient power ($1-\beta=0.80$ using $\alpha=.05$) to detect a mean difference between groups of 0.25 mm in joint space narrowing over the 84-month study period. This estimated difference is based on the following rationale. Previous studies have shown that patients with primary OA exhibit an estimated 0.3-mm change in joint space width per year^{51,63}. Since we will be studying patients at the time of OA onset, we will assume that patients who undergo initial changes will exhibit an average joint space narrowing of 0.1 mm per year, or a total of approximately 0.6 mm over the 84 months. This estimate was conservatively adjusted based on the study by Johma et al, who found that only 50% of the subjects that undergo ACL reconstruction after injury exhibit early degenerative changes following surgery⁵⁰. After taking into account that only a subset of subjects randomized may exhibit OA, the resulting mean difference is decreased to be 0.25-0.30 mm over the 84-month study period. An additional consequence of only a subset of the patients that are randomized exhibiting degeneration is an increase in the variability encountered across subjects with respect to joint space narrowing. The variability estimate used in our computations ($\sigma_{\Delta}=0.35$ mm) resulted from increasing the estimate derived from the literature for a group of subjects with OA in order to reflect our expected mixture of two subsets of subjects. Based on each subset having $\sigma_{\Delta}=0.20$, with 50% of the patients exhibiting narrowing a total of 0.6 mm and 50% showing no degeneration, the resulting overall estimated $\sigma_{\Delta}=0.35$. Assuming joint space width at baseline is approximately 4.5 mm³⁰, this detectable mean difference (0.25 mm) represents an approximate 5% change between the treatment groups in the mean rate of degeneration. We recruited 54 subjects per group in an effort to have 46 assessable subjects per group at the three-year follow-up visit based on the estimated 15% dropout rate^{4,7}. We have more than met this goal (3% drop out in our treatment groups and 15% drop out in our control group at 3 years). For the proposed 180-month follow-up we expect that we will have at least 35 patients/subjects in each group (20% drop out rate of subjects currently enrolled).

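### State that variance is not pooled across the two reconstructed arms and the uninjured controls: if it is, high versus low at 180 months runs at about 4.6% to 10% instead of 5%, depending on how many controls narrow

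*Combined protocol and SAP*

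**What the plan says.** Section 8 (Treatment Comparisons - Primary Outcome Measure) specifies one repeated-measures model for joint space width. Its fixed factors are group (low tension, high tension, control), "limb (operative vs. contra-lateral or two controls), location (medial vs. lateral"), time, and their interactions. The listed time levels end at 84 months. PROC MIXED is chosen because it "allows for covariance structures other than compound symmetry (e.g. unstructured, autoregressive, spatial power law"). The reason given is that "It is expected that the variability across subjects may increase across time due to only a subset of individuals exhibiting degeneration". After a significant interaction, "simple effects will be compared using the Student-Newman-Keuls procedure based on the appropriate error terms". Normality of residuals is to be checked and the data transformed if necessary.

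The sample-size justification applies the same mechanism to the patients: "An additional consequence of only a subset of the patients that are randomized exhibiting degeneration is an increase in the variability encountered across subjects". Its SD of 0.35 mm comes from a within-subset SD of 0.20 mm "with 50% of the patients exhibiting narrowing a total of 0.6 mm and 50% showing no degeneration". Section 2 describes the controls as people "who had no known history of knee injury or symptoms of arthritis".

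The hypothesis in section 1 compares each arm with control: high tension is to equal control, while joint space in the low-tension "treatment group will be significantly less than that of the control group 15 years after surgical reconstruction of the ACL". No section says whether covariance is common to the three groups or estimated by group.

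**The concern.** The structures named as examples let variance change over visits. In PROC MIXED, however, one set of covariance parameters serves all groups unless a by-group option is requested. A mixture of narrowing and stable knees raises variance in whichever group contains it, so the plan's own argument applies between groups as well as over time. If a third of the pooled variance comes from controls who mostly do not narrow, it is too small for the reconstructed arms and too large for the controls.

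Two things are at stake. High versus low is the only randomised comparison, and its standard error would be too small if both arms degenerate. The arm-versus-control contrasts that form the stated hypothesis would also be mis-sized, in a direction that depends on which groups degenerate. The closing note of section 8 says the 7-year results are already published, so the point concerns the 144- and 180-month analyses.

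**Working it through.** **Inputs from the sample-size justification.** Within-subset SD 0.20 mm; 50% of a reconstructed arm narrows; 0.6 mm over 84 months, or 0.1 mm per year; at least 35 per group at 180 months; alpha 0.05 (two-sided assumed).

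**Assumptions not in the documents.** Narrowing T at 180 months is 0.6 × 180/84 = 1.29 mm, or 0.1 × 15 = 1.5 mm. Half of reconstructed knees still narrow, the subset SD stays at 0.20, and a share p of controls narrows by the same T, with p from 0 to 30%.

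**The plan's own figure first.** The mixture variance at 84 months is 0.20² + 0.5 × 0.5 × 0.6² = 0.04 + 0.09 = 0.13, so the SD is 0.361; the plan prints 0.35. With 35 per group and a 0.25 mm difference, two-sided t-test power is 0.816 with SD 0.361 and 0.838 with SD 0.35. The stated 0.80 is therefore reproduced approximately from the mixture.

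**Case 1: both arms degenerate alike, one variance for three groups.**

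- Arm variance: V_A = 0.04 + 0.25T²
- Control variance: V_C = 0.04 + p(1 − p)T²
- Pooled variance, equal group sizes: V = (2V_A + V_C)/3
- High-low error, unadjusted: 2[1 − Φ(1.96 √(V/V_A))]
- Arm-control error: 2[1 − Φ(1.96 √(2V/(V_A + V_C)))]

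For T = 1.5 and p = 0: V_A = 0.6025, V_C = 0.04, V = 0.415, √(0.415/0.6025) = 0.830, and 2[1 − Φ(1.627)] = 10.4%.

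The Student-Newman-Keuls and arm-control columns are simulations of the mixture (100,000 trials, 102 df, critical values 3.364 and 2.805). Ranges cover T = 1.29 and 1.5.

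| Controls narrowing | Control SD (T = 1.5) | High-low, unadjusted (formula) | High-low, Student-Newman-Keuls | Arm-control |
|---|---|---|---|---|
| 0% | 0.20 | 10.2-10.4% | 10.1-10.3% | 2.7-2.9% |
| 10% | 0.49 | 7.9% | 8.0-8.1% | 3.7-3.8% |
| 20% | 0.63 | 6.4-6.5% | 6.2-6.4% | 4.2-4.3% |
| 30% | 0.72 | 5.6% | 4.5-4.6% | 4.7-4.9% |

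With variance taken from the two randomised arms only (68 df), the unadjusted high-low error was 4.9-5.1% in every row.

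**Case 2: high tension fully protects, so high and control share the same p.** Now V = (V_A + 2V_C)/3. For T = 1.5 and p = 0, V = (0.6025 + 0.08)/3 = 0.2275, against a true mean variance for low-control of 0.3213. Since √(0.2275/0.3213) = 0.842, nominal 95% intervals miss 9.9% of the time. Simulation gives low-control misses of about 10%, 7% and 6%, and high-control misses of about 0%, 1.5% and 3.4%, for p = 0, 10% and 20%.

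**Sensitivity (high-low, unadjusted).**

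- Subset SD 0.50 instead of 0.20, no controls narrowing: 8.1% (T = 1.29) or 8.6% (T = 1.5).
- 75% of reconstructed knees and 30% of controls narrowing: 4.6%.
- Unequal sizes, T = 1.5, no controls narrowing: 9.7% with 40 per arm and 35 controls; 12.3% with 35 per arm and 48 controls.
- Neither arm degenerating: 5%.

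**Link to the full model.** These are change-score calculations. With complete data and saturated means over limb, location and visit, a common unstructured covariance gives the same standard error as the change score. With missed visits the figures are approximate.

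**The case against.** The strongest reply is that the plan contains no stated error. Its covariance structures are examples, its reference to appropriate error terms would permit a by-group covariance, and it recognises that homogeneity will fail. That stands. A reader might infer that the analysis will pool, or that the published 84-month analysis was wrong; the documents say neither.

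A reader might also infer that high versus low is inflated across the whole range of control narrowing, because the unadjusted contrast never falls below 5.6% in the table. Under the planned Student-Newman-Keuls procedure this is not so: the error is below 5% when 30% of controls narrow. The documents give no control narrowing rate, and the 10% end needs essentially none over 15 years.

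Nor is the stated hypothesis test generally anti-conservative. It compares each arm with control, and those tests are conservative when both arms degenerate alike. Low-control intervals become too narrow when high tension protects, and the excess is about one point if 20% of the high-tension and control groups narrow.

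The planned residual check and transformation do not answer the point. They are aimed at distributional shape, and a transformation cannot be relied on to equalise variances that differ because only some knees narrow.

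Finally, the repair needs care, because some simple versions do worse than pooling. This is why the fix carries conditions.

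**Conclusion.** The point holds as a cheap improvement to an open specification, with medium confidence. Followed with software defaults and the plan's own mixture, section 8 gives a mis-sized randomised comparison at 180 months: about 10%, 8% or 6.3% under Student-Newman-Keuls when 0%, 10% or 20% of controls narrow, and no excess at 30%. If high tension protects instead, the error moves to the arm-versus-control intervals, too narrow for low-control and too wide for high-control.

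The size is conditional on pooling actually being used, on the assumed control share, on extrapolating narrowing and its 50% prevalence to 15 years, on a constant subset SD, and on 35 per group. The sensitivity results show that it can shrink, vanish or, with a larger control group, grow somewhat. The documents do not support a stronger claim, such as a declared pooling error or a uniform inflation.

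**What to change.** Amend section 8 before the 144- and 180-month data are analysed:

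1. Add 144 and 180 months to the time factor. Without them the written model contains no 15-year contrast.
2. State that variance is not pooled across the three groups. Base high versus low on variance from the two randomised arms only. Base each arm-versus-control contrast on the variances of the two groups compared, and use these standard errors in the pairwise procedure in place of a single pooled error term.
3. Keep low, high and control as three separate variance groups. Merging the two reconstructed arms makes low-control intervals miss 13.7-14.3% at 180 months if high tension fully protects and no controls narrow.
4. Let variance differ by limb and location. In model-fitting checks on complete simulated data, a slope variance common to operated and contralateral knees gave 16-26% high-low error; freeing it by limb and location in the reconstructed arms gave 4.7-6.0%.

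The cost is a few sentences, with no new data and no change to the outcome; the fixed factors stay as planned apart from the added visits. The downside is some loss of degrees of freedom (68 instead of 102 for high versus low in the simple case) and a few more covariance parameters. A low-parameter structure is needed: a full unstructured matrix over 2 limbs × 2 locations × 6 visits has 24 × 25/2 = 300 parameters per group.

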5.5. Clinical outcome

Clinical outcome will be assessed using the International Knee Documentation Committee (IKDC) knee rating scale^{23,48}. The IKDC rating has been validated for ACLR⁴⁸. The IKDC scores evaluate four categories: 1) the patient's subjective assessment of function, 2) symptoms, 3) range of knee motion, and 4) clinical examination. The IKDC score rates knees as normal, nearly normal, abnormal, and severely abnormal, which can be transformed to an ordinal scale of 1 (normal) to 4 (severely abnormal). The final IKDC rating is then based on the score of the worst category⁴⁸. In addition, height, weight, body mass index, thigh circumference (6cm above joint line) and the number of recurrent injury episodes is recorded. A sports medicine physician and a physical therapist will continue to independently perform all of the pre- and post-operative clinical examinations.

6. Controlled Variables

Investigators have shown that the initial graft tension level required to restore normal knee laxity is specific to the graft material, cross-sectional area of the graft, and the free length of the graft between fixation sites¹⁵, and these were controlled in this study. Initially, subjects undergoing ACL reconstruction using a bone-patellar tendon-bone autograft were recruited to control the variability due to graft type. However, there has been a recent surge in the popularity of the 4-stranded hamstring tendon graft. Thus, we elected to recruit patients who were candidates for ACL reconstruction with 4-stranded hamstring autografts to increase our population base. This was justified because recent biomechanical studies have demonstrated that the structural properties of the patellar tendon autograft are equal to that of the 4-stranded hamstring tendon autograft⁷⁹. Likewise, the in-situ forces, the passive load-displacement response, and dynamic kinematics of reconstructed knees with patellar tendon and 4-stranded hamstring tendon grafts are similar^{68,82}. Finally, recent prospective randomized clinical trials have shown that functional outcome following ACL reconstruction with 4-stranded hamstring or patellar tendon autografts are equivalent^{2,3,19,33,34,41,42,49,57,62,64}.

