Treatment Comparisons - Secondary Outcome Measures: Repeated measures analyses of variance will also be used to test for differences in secondary outcome measures corresponding to knee kinematics, dynamic function, patient reported outcomes, and clinical outcomes. For measures that are performed on each limb (e.g. A-P laxity), the statistical model will include fixed factors representing treatment group, limb, and time, along with their interactions. Repeated measures analyses on secondary outcome that are not limb-specific (e.g. KOOS and SF36) will include only treatment, time, and their interaction as factors. Post hoc analyses involving tests of simple effects and orthogonal polynomials will be similar to methodology previously described for joint space width. Because specific secondary outcome measures are assessed more frequently in the two experimental arms than in the control group (Tables 2&3), direct post hoc comparisons involving the two tension groups and examination of temporal trend in these group will utilize the additional assessments.

Relationship between A-P Laxity and Progression of OA: The longitudinal relationship between A-P laxity and progression of OA as measured by joint space narrowing (both radiographically and using MRI) will be examined in the context of hierarchical linear modeling¹³, also known as random coefficient modeling. Using data obtained from the experimental subjects, SAS PROC MIXED will be employed to examine the association between individual subjects' changes in A-P laxity with their changes in joint space width (radiography) or cartilage thickness (MRI). This will be accomplished by considering A-P laxity as a covariate (predictor) that would potentially change over time with joint space width and cartilage thickness being considered as the dependent measures. Individual subjects are modeled based on unique intercepts and slopes corresponding to time and the covariate. Across subject factors such as tension group, gender, graft type, and age will also be considered. A similar analysis will be performed to establish the relationship between isokinetic strength, KOOS, functional testing and OA progression.

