Power for Secondary Outcome Measures: Having determined the number of subjects needed to have sufficient power to detect expected differences in joint space narrowing, we computed the magnitude of the detectable difference for the main secondary outcome measures. These estimates are based on our previous data and values found in the literature. When the estimates were based on cross-sectional data from the literature (i.e. isokinetic strength), moderate correlation across time was assumed ($r=0.50$). The following mean differences correspond to the estimated power=0.80 and $\alpha=.05$ with the proposed sample sizes: A-P laxity =

1.25 mm (a 16% change relative to the normal A-P laxity value ⁷²); isokinetic knee strength = 18.5 Nm (a 12% change relative to normal, a “mild” deficit ¹⁶); KOOS- QOL score = 10.5 (a 10% change relative to full scale, considered less than a mild deficit ⁵⁹); KOOS-sports score = 10.1 (a 10% change relative to full scale, considered less than a mild deficit ⁵⁹), and IKDC score = .50 (a 12% change relative to normal ⁴⁸).

Note (9/29/2017): The 7 year data were completed and published in the American Journal of Sports Medicine in January 2016 (<http://www.ncbi.nlm.nih.gov/pubmed/27159308>). The study was extended to 12 and 15 years and the data collection for these time points is currently underway.

REFERENCES

1. Aickin M. A program for balancing the allocation of subjects in a clinical trial. *Computational Biomed Res.* 1982;15:519-524.

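### The IKDC detectable difference of 0.50 is not 12% of normal on the plan's 1-to-4 coding, and the three-group ANOVA should not let near-constant controls set the error term

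*Combined protocol and SAP*

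**What the plan says.** Section 8, under Power for Secondary Outcome Measures, lists detectable mean differences at "estimated power=0.80 and $\alpha=.05$ with the proposed sample sizes". The last item is "IKDC score = .50 (a 12% change relative to normal". No SD is given for it. The sample-size paragraph just before uses "The estimated sample size of 35 assessable subjects per group through the 84-month study period".

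Section 5.5 defines the measure: "Clinical outcome will be assessed using the International Knee Documentation Committee (IKDC) knee rating scale". Knees are rated in four ordered classes, "which can be transformed to an ordinal scale of 1 (normal) to 4 (severely abnormal"). It adds: "The final IKDC rating is then based on the score of the worst category". Each knee therefore takes one of four integer values.

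For the analysis, section 8 (Treatment Comparisons - Secondary Outcome Measures) states: "Repeated measures analyses of variance will also be used to test for differences in secondary outcome measures". The measures covered include "dynamic function, patient reported outcomes, and clinical outcomes". No ordinal or rank-based method is named for IKDC.

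**The concern.** The percentage and the coding cannot both be right as written. The same list describes a 12% change in isokinetic strength relative to normal as a mild deficit, so a reader may take the IKDC 12% as equally small, when it stands for half a grade.

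The second issue is the error term. The ANOVA has three groups: two of reconstructed knees and one of volunteers screened for no known knee injury or arthritis symptoms (section 2). On a rating with a floor at 1, the volunteers may vary very little. If one residual variance is shared by all groups, their small spread lowers the standard error for high- versus low-tension, the only randomised comparison, and that test would reject too often.

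**Working it through.** **1. The percentage.** Inputs: difference 0.50 and stated 12% (section 8); normal = 1, worst = 4 (section 5.5).

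| Denominator | Calculation | Result |
|---|---|---|
| Worst score, 4 | 0.50/4 | 12.5% |
| Range, 4 − 1 = 3 | 0.50/3 | 16.7% |
| Midpoint, 2.5 | 0.50/2.5 | 20.0% |
| Normal, 1 | 0.50/1 | 50.0% |

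Working backwards, 0.50/0.12 = 4.17, so the stated figure needs a denominator near 4. Only the worst score fits. The KOOS-QOL item in the same list shows 10.5 out of 100 as 10%, so 12.5% shown as 12% would follow the same truncation. A full-scale divisor carrying the wrong label is the likely origin, but that is an inference.

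**2. The SD behind 0.50.** The plan gives none, so 0.50 cannot be verified, only inverted. Assume a two-sided test (sidedness is not stated) and two equal groups:

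SD = 0.50 / [(1.960 + 0.842) × √(2/n)].

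- n = 35: 0.50 / (2.802 × 0.239) = 0.75 (0.74 with the t distribution)
- n = 46: 0.86
- n = 54: 0.93

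The power statement does not say which n was used for IKDC. None of these values is impossible on a 1-4 scale. If the SD is cross-sectional, the variance on this scale cannot exceed (mean − 1)(4 − mean). An SD of 0.74 (variance 0.548) therefore needs a mean of at least about 1.2, since 0.195 × 2.805 = 0.547. A group sitting almost wholly at grade 1 could not have that SD.

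**3. Effect of a pooled error on high versus low tension.** Take one visit, three equal groups, SD s in each tension arm and c in controls.

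- Pooled variance = (2s² + c²)/3.
- The test statistic is inflated by s/√(pooled variance).
- Type I error ≈ 2 × [1 − Φ(1.96 / inflation)].

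The plan gives no IKDC grade distribution, so these SDs come from assumed ones:

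| Assumed proportions in grades 1/2/3/4: controls; each tension arm | c, s | Pooled variance | Inflation | Type I error |
|---|---|---|---|---|
| .40/.40/.15/.05; .20/.35/.30/.15 | 0.85, 0.97 | 0.868 | 1.04 | 6.0% |
| .30/.50/.15/.05; .15/.35/.35/.15 | 0.80, 0.92 | 0.778 | 1.04 | 6.0% |
| .85/.15/0/0; .55/.30/.10/.05 | 0.36, 0.85 | 0.525 | 1.17 | 9.5% |
| All controls at grade 1 (limit) | 0, s | 2s²/3 | 1.22 | 11.0% |

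Simulating the first three rows with 35 per group gave 6.0%, 6.0% and 9.6%. Using only the tension arms' own variance gave 5.0-5.1% throughout.

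**4. Mean-based against rank-based test.** With 35 per group, comparing the control and tension distributions in rows 1, 2 and 3 (mean shifts 0.55, 0.55 and 0.50), power of the t-test against the Mann-Whitney test was 0.68 vs 0.67, 0.74 vs 0.74, and 0.92 vs 0.86.

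**The case against.** The strongest reply is that this is a slip in a label. The 0.50 is printed beside the percentage, section 5.5 gives the scale, and the trial is sized on joint space narrowing. That stands: no sample size or decision changes.

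A reader might infer that the trial is about four times less sensitive on IKDC than it claims, because 0.50 is 50% of the code for normal. The documents do not support this. Sensitivity is the absolute difference, which is stated and not shown to be wrong. The factor of four comes only from dividing by the code 1. A ratio to an ordinal code is arbitrary; coded 0 to 3, it would be undefined. Replacing 12% with 50% would swap one uninformative figure for another. Against the range, the gap is 16.7% versus 12.5%, a factor of 1.33.

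A reader might also infer that ANOVA is invalid for a four-level rating and must be replaced by a cumulative-logit model. That is not shown either. In the assumed distributions the mean-based test was at most trivially less powerful than the rank test, and more powerful where most controls were normal. If nearly all controls are rated 1, a cumulative-logit model meets separation, and its control contrasts may not be estimable. A GEE version would ordinarily need a stricter missing-data assumption than the likelihood-based handling the plan chose.

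Finally, the plan does not state a common variance in so many words. For joint space width it allows covariance structures other than compound symmetry, checks residual normality and permits transformation. This is partial mitigation. It is written for the primary outcome and anticipates variance changing over time, not differing by group, and no transformation removes the ties and floor of a four-level rating. That controls cluster at grade 1 is plausible from their screening, but no IKDC data are given.

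**Conclusion.** The 12% label is wrong on the plan's own coding and corresponds only to division by the worst score. The detectable difference is best read as half a grade, about 17% of the range. The 0.50 and the trial's sample size are not shown to be wrong.

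The analysis point holds in a limited form: unless residual variance may differ by group, the high- versus low-tension comparison of IKDC can be anti-conservative. The estimate of about 6-10% instead of 5% rests on assumed grade distributions, equal group sizes, a single visit and one residual variance pooled over three groups. It vanishes if controls vary as much as patients. This is a minor correction to one secondary outcome.

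**What to change.** - **Power statement.** Give the IKDC difference as 0.50 grade on the four-grade (1-4) scale, about 17% of the 3-point range. State the SD and n behind it; at 35 per group the implied SD is about 0.74-0.75 under the assumptions above.
- **ANOVA for IKDC.** Allow a separate residual variance for each group (in PROC MIXED, through the GROUP= option of the REPEATED statement), or compare the tension arms using only their own variance.
- **Reporting.** Tabulate the proportion rated normal or nearly normal by group and visit. Add a cumulative-logit model as a sensitivity analysis, restricted to contrasts it can estimate.

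The cost is slightly wider intervals and one extra table for one secondary outcome. The mean-based analysis stays the main one. The changes should be written down before the 144- and 180-month analyses.
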